12.4 Organs at risk

The organs at risk (OARs) that must be contoured for CHARIOT and the naming convention used in naming these structures are detailed below. The spinal cord should be outlined on slices which include or are within 20mm of the PTV in the superior and inferior directions and a Planning Risk Volume (PRV) for the cord is created to account for positioning error. The full extent of the right and left lungs are outlined, this should be done in such a way that the planning system will be able to calculate a combined lung dose volume histogram (DVH). The whole heart is outlined to the extent of the pericardial sac (if visible). The major blood vessels (superior to the organ) and the inferior vena cava (towards the inferior extent of the heart) are excluded. The whole liver is outlined if the level of its superior edge overlaps with the level of the inferior extent of the PTV. Each kidney is outlined separately if the level of its superior edge overlaps with the level of the inferior extent of the PTV. The whole stomach should be outlined in such a way that a stomach DVH can be produced

12.5 Treatment Plan Optimisation

A single phase IMRT plan (or equivalent if using 3D Conformal approach) should be produced for patients treated in Stage A1 and an inverse-planned IMRT treatment plan should be produced for patients treated in Stage B. Type B algorithms (e.g., collapsed cone, AAA) must be used for dose calculation.

12.6 Dose constraints

Stage A1

All constraints corrected using the linear quadratic equation and are valid only for 35Gy/15# and should not be corrected

Structure	Naming convention*	DVH constraint
PTV	PTV	D99% > 95% V95% > 99%
ICRU Maximum Dose	Please label patient outline as "External"	D1.8cc < 107%
Spinal Cord PRV	SpinalCord_PRV	None
Heart	Heart	Dmean < 23Gy V28Gy < 45%
Combined lungs	Lungs	Dmean < 15Gy V18Gy < 25%
Stomach	Stomach	None
Liver	Liver	Dmean < 26Gy V28Gy < 30%
Individual kidneys	Kidney_L and Kidney_R	V18Gy < 25%

Stage B:

The following dose objectives (Warren et al., 2014) and nomenclature (Santanam et al., 2012) should be used:

Structure name	Constraint	Optimal	Mandatory
PTV	V95% (47.5Gy)	> 95%	≥ 90%
	Dmedian	100%	The median should be between 98-102% of the prescription dose.
External	D1.8cc		<107% of highest prescribed dose
SpinalCord_PRV	D0.1cc	< 40Gy	< 42 Gy
Heart	Dmean V30Gy	< 25Gy < 45%	<30Gy -
Lungs (Combined lungs)	Dmean V20Gy	< 17Gy < 20%	<19Gy ≤25%
Stomach_excl_PTV (Stomach excluding PTV)	V50Gy	< 16cc	< 25cc
Liver	Dmean V30Gy	≤28Gy < 30%	≤30Gy -
Kidney_L and Kidney_R (Individual kidneys)	V20Gy	< 25%	≤30%

12.7 Treatment delivery and verification

The treatment should be delivered in a single IMRT (or 3D Conformal approach in Stage A1 only) given the target volume described and the normal tissue constraints above, it is up to the individual participating centre to decide the field arrangements. It is recommended that the best available positional verification methods should be used to ensure correct delivery.

Stage A1

The use of cone beam CT matched to planning CT scans is recommended. The minimum on-treatment verification is for imaging the initial three fractions so that a correction for systematic error can be applied and then continue with weekly imaging. The isocentre should be moved if disagreement is seen in excess of agreed tolerance levels based on local study – typically 5mm.

Stage B

The use of cone beam CT matched to planning CT scans is mandated.

The minimum protocol for verification is on-line imaging of the initial five fractions so that a correction for systematic error can be applied and then continue with minimum weekly imaging thereafter for Stage B patients. The isocentre should be moved if disagreement is seen in excess of agreed tolerance levels based on local study – typically 5mm.

12.8 Management of radiotherapy toxicity

Radiotherapy interruptions will usually not be necessary. However, if radiation is held for any reason, all systemic therapy must also be held, including M6620 (Berzosertib). Interruptions may be kept to a minimum by the use of ancillary therapy and vigorous nutritional support. Interruptions are permitted only on the basis of toxicity. However, if the RT interruptions are due to either technical reasons or due to bank holidays, the schedule should be made up to account for this either on a Saturday or at the end of the treatment.

Toxicity	Radiotherapy treatment interruption required:	Restart radiotherapy:
Oesophagitis	Grade 4; see management of symptoms below. Aim to limit interruption to 3 treatment days (fractions).	
Haematological toxicity		
Neutrophils	Stop RT treatment if neutrophils $<0.5 \times 10^9/L$ or	If levels recover to $0.5 \times 10^9/L$ (neutrophils) and $25 \times 10^9/L$ (platelets)
Platelets	platelet count $<25 \times 10^9/L$ and monitor every 48 hours. Note: systemic therapy should be interrupted initially as per local policy.	
Non-Haematological toxicity		
All toxicities	Grade 3: stop systemic treatment first and aggressive management should be pursued as per protocol, if no recovery to \leq grade 2 within 48h, consider withholding radiotherapy as follows:	
Vomiting	≥ 6 episodes of vomiting (\geq grade 3) lasting ≥ 3 days and unresponsive to antiemetics	Resolves to \leq grade 2
Diarrhoea	An increase from a patients usual bowel habit of ≥ 7 watery stools/day (\geq grade 3) and unresponsive to antidiarrhoeals	Resolves to \leq grade 2
Weight loss	Loss $\geq 10\%$ (\geq grade 2) of pre-treatment weight	
Other ¹	Grade 3: withhold radiotherapy and chemotherapy	Resolves to \leq grade 2

¹Rarely, non-treatment related or unexpected toxicities may require interruption of therapy at the discretion of the treating oncologist. Interruption of therapy may continue until the toxicity has regressed to \leq grade 2 to allow resumption of therapy; however, every effort should be made to limit treatment interruptions to 1-2 weeks

Oesophagitis

If Grade 4 oesophagitis occurs, and a treatment interruption is being considered, every effort should be made to limit it to 3 treatment days or less. Patients requiring hospitalization because of oesophagitis may have their treatment interrupted. Acute oesophageal toxicity, which typically can occur within 2 weeks of the initiation of treatment and manifests as dysphagia, odynophagia, reflux symptoms, etc. should be pharmacologically managed with the following approach and should be initiated at the first signs or symptoms of oesophageal toxicity. Double PPI dose or start PPI, soluble paracetamol, oramorph, fluconazole and follow local policy. If a patient develops grade 3 oesophagitis in the last week of treatment (i.e., with 5 or fewer radiation treatments remaining), radiation therapy (but not chemotherapy) may continue at the discretion of the treating physician.

If interruption of therapy (< 2 weeks) becomes necessary, radiation therapy should be completed to the prescribed doses. If treatment restarts and there are week-ends left aim to compensate for days lost with treatment Saturdays. No BID fractionation is permitted.

Total number of fractions and elapsed days should be carefully reported. If an interruption of more than 2 weeks is necessary, resumption of treatment is at the discretion of CI. The patient's treatment plan will be considered a major deviation, but follow-up will be continued. Any toxicity that requires a dose reduction must be documented in the patient notes.

12.9 The management of unscheduled gaps in radiotherapy treatment

In the event of unscheduled gaps to radiotherapy treatment, these should be managed as described above (section 12.8)

CHARIOT patients should be managed as Category 1 patients in Stage B and Category 3 in stage A.

Where possible during concurrent chemoradiotherapy phase patients should continue with RT if unable to tolerate chemotherapy in Stage B. Patients should be withdrawn from trial if RT is delayed by greater than 2 weeks.

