5.5.2 Stage B evaluations on early withdrawal

Where possible, patients will be followed up as per the follow up visits which should be brought forward to 1, 7 and 13 weeks post end of treatment, including assessments of AEs and DLTs see section 6.

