18 STATISTICAL ANALYSIS PLAN

For all analyses, patients will be included according to the treatment to which they are assigned. All patients, regardless of how much treatment received and follow-up completed, will contribute to analysis.

It is therefore important that every effort is made to encourage patients, including those patients who do not receive/complete their allocated treatment, to attend for follow-up clinic visits to avoid bias in the analysis of the results.

A detailed statistical analysis plan will be available from the time the first patient is recruited and will be finalised before any analysis is undertaken. The analysis plan will be written in accordance with the current OCTRU standard operating procedures and will be finalised and agreed by the trial statistician and the CI. Sites must report any unintended deviations/violations to OCTO according to the procedure outlined during site initiation training.

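### Protocol 12.8 and 12.9 conflict for radiotherapy gaps of more than two weeks, and 12.9 does not say whether withdrawal is from treatment or from the study

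*Protocol*

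**What the plan says.** Protocol 12.8, on an interruption of more than two weeks: "If an interruption of more than 2 weeks is necessary, resumption of treatment is at the discretion of CI". It continues: "The patient's treatment plan will be considered a major deviation, but follow-up will be continued".

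Protocol 12.9 opens by sending unscheduled gaps to 12.8 for their management. It ends: "Patients should be withdrawn from trial if RT is delayed by greater than 2 weeks". It does not mention follow-up, and the sentence is not limited to one stage.

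Other sections bear on what withdrawal means:

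- Section 6 describes two kinds. Stopping treatment early (6.1) moves the patient into routine follow-up. Withdrawing consent (6.2) lets the office close the remaining CRFs.
- Section 5.5.2, for early withdrawal in Stage B: "Where possible, patients will be followed up as per the follow up visits which should be brought forward to 1, 7 and 13 weeks" after the end of treatment, with AE and DLT assessment. Section 5.4.2 does the same for Stage A1 at 1, 6 and 9 weeks.
- Section 20.2 requires follow-up according to the protocol for a patient who withdraws from the study.
- Section 18: "All patients, regardless of how much treatment received and follow-up completed, will contribute to analysis". It then asks sites to keep patients who do not complete treatment coming to follow-up, to avoid bias.

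**The concern.** The two sections cover the same event and differ on treatment. One allows resumption at the Chief Investigator's discretion; the other takes the patient out. Section 12.9 therefore also conflicts with the section it adopts. The change of word from interruption to delay does not separate them, because 12.9 is about unscheduled gaps.

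The second problem is the wording of the withdrawal, which matches neither category in section 6. Where the protocol means treatment only, it says so: the renal-function tables in 9.4.3 and 9.4.4 withdraw patients from trial treatment and ask for CRFs to continue, and section 15 specifies trial treatment for pregnancy. Section 12.9 has no such qualifier, so a site could reasonably read it as off-study.

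Section 12.8 states that "Interruptions are permitted only on the basis of toxicity", with technical and bank-holiday gaps to be made up. Patients with a gap this long would therefore often have serious toxicity. If they left the study, the missing outcomes would be unlikely to be missing at random.

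**Working it through.** There is no figure in the plan to reproduce. The check compares the texts and then asks what an off-study reading would cost.

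**1. The instructions side by side**

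| Gap of more than 2 weeks | 12.8 | 12.9 |
|---|---|---|
| Treatment | May resume, Chief Investigator decides | Withdrawn (after deferring to 12.8) |
| Follow-up | Continues | Not stated |

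**2. Is the delay already a DLT?** Two weeks of weekday treatment is 2 × 5 = 10 fractions, or 14 days. The triggers in 9.1.2 are a completion delay of more than one week (Stage A1), more than 3 consecutive fractions (Stage B), and 7 days or more for any of the treatments (both). The gap exceeds all of them. Two conditions remain: toxicity must be the cause, and under 9.1.1 it must be considered related to M6620 or to its interaction with radiotherapy or chemoradiotherapy.

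**3. Effect on the primary model.** SAP 3.1.1 gives weight w = 1 if a DLT has occurred, and otherwise w = ½(u/T + v/D), where u is time observed, T the DLT window, v the M6620 received and D the M6620 planned.

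- If the delay is a DLT, w = 1. Later follow-up does not change that patient's contribution. This SAP version omits the Stage B design, but DLT status is binary and would already be set.
- If the delay is not a DLT (technical cause, or toxicity judged unrelated), follow-up matters. As an illustration for Stage A1, take T = 63 days (9 weeks), assume the last radiotherapy is on day 3 or day 12, no later M6620, and observation ending 14 days after that. Dosing days come from Protocol Table 8.1.

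| Schedule | Last RT day | v/D | w if observation stops | w if followed to week 9 |
|---|---|---|---|---|
| 1 | 3 | 1/3 | ½(17/63 + 1/3) = 0.302 | ½(1 + 1/3) = 0.667 |
| 3 | 3 | 1/6 | ½(17/63 + 1/6) = 0.218 | ½(1 + 1/6) = 0.583 |
| 1 | 12 | 2/3 | ½(26/63 + 2/3) = 0.540 | ½(1 + 2/3) = 0.833 |
| 3 | 12 | 4/6 | ½(26/63 + 4/6) = 0.540 | ½(1 + 4/6) = 0.833 |

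The weight lost is ½(63 − 17)/63 = 0.365 for day 3 and ½(63 − 26)/63 = 0.294 for day 12. In addition, a DLT occurring after such a patient left would be missed and the patient would stay in the model as a partial non-event.

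**4. Secondary data exposed.** In Stage B, radiotherapy ends at week 11 if on time, and late DLTs are those with onset from 6 weeks later: 11 + 6 = week 17. The last visit is week 24, so the late-toxicity window is 24 − 17 = 7 weeks, within a post-radiotherapy period of 24 − 11 = 13 weeks. Week-24 CT, endoscopy and biopsy, PFS and OS are also exposed. In Stage A1, the exposed items are the week-12 CT and the 6- and 12-month reports. Late DLTs are defined for Stage B only.

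**5. Share of patients.** One patient is 1/20 = 5% of the Stage A1 maximum and 1/25 = 4% of the Stage B maximum. Stage A2 has no radiotherapy. These are shares of patients, not effects on an estimate.

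**The case against.** A reader might infer that following 12.9 necessarily discards the follow-up of the most toxic patients and so biases the DLT estimate. The documents do not support that.

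- Sections 5.4.2 and 5.5.2 keep AE and DLT visits after early withdrawal, 6.1 moves patients who stop treatment into follow-up, 20.2 requires follow-up of withdrawn patients, and only consent withdrawal closes CRFs. Loss of follow-up is one literal reading of one sentence, against all of these and 12.8 itself.
- The patients most affected by treatment toxicity would normally already count as DLTs.
- Not every long gap is toxic: 12.9 covers all unscheduled gaps, and 8.7 mentions machine breakdowns.
- Section 18's inclusion rule does not contradict 12.9, since it expressly accommodates incomplete follow-up.

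All of this stands and limits the point. It does not remove it. The conflict over resumption is untouched by any follow-up provision. The visits in 5.4.2 and 5.5.2 are to be held only where possible. Section 12.9 still lacks the treatment-only wording used in 9.4.3 and 9.4.4.

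**Conclusion.** The contradiction between 12.8 and 12.9 is real: a site with such a patient cannot comply with both. The loss of follow-up is a possible result of an off-study reading, not something the protocol states.

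The exposure is mainly secondary. It would also be wrong to infer that Stage B could lose 13 weeks of late-toxicity assessment; the late window is about 7 weeks. The primary endpoint is largely protected, apart from patients whose delay is not itself a DLT.

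This rests on three assumptions: that the unrestricted sentence in 12.9 applies to Stage A1 as well as Stage B; that Stage B radiotherapy is on time for the week-17 figure, which would shift for a patient who stops early or resumes late; and that the Stage A1 weights are illustrative only. The documents give no expected frequency for gaps this long, and 12.8 expects interruptions to be usually unnecessary. The point is worth correcting because the instructions conflict for a serious safety event and the correction is small.

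**What to change.** Reconcile 12.8 and 12.9 to a single treatment instruction for gaps of more than two weeks. Which instruction is a clinical decision for the sponsor and investigators, and this review does not choose it.

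In 12.9, state that any withdrawal is from trial treatment, and that DLT, response and survival follow-up and CRF completion continue unless the patient withdraws consent. Cross-refer to 5.4.2, 5.5.2 and 6.1.

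The cost is about one sentence in 12.9, with 12.8 aligned if needed. No visit, assessment or analysis is added, because those sections already provide for this follow-up.

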12.10 Radiotherapy quality assurance

In the first instance, any queries regarding radiotherapy quality assurance for CHARIOT should be addressed to the national Radiotherapy Trials QA group (RTTQA) contact ([contact] or www.rtrialsqa.org.uk).

Centres accredited for SCOPE2 can take part in the trial with no further pre-trial QA required, as these centres will have already completed an outlining and planning exercise, and submitted a process document for review by RTTQA.

Real time review of all patients will not be required instead there will be timely retrospective review of radiotherapy plans in the event of any unexpected or severe toxicity. All images, outlines, plan and dose data (DICOM) should be submitted to the RTTQA contact who will co-ordinate review of the data to check protocol compliance.

13 EVALUATION OF RESPONSE

13.1 Tumour assessment

A clinical and radiological evaluation of malignancy, as judged appropriate by the Investigator, and in line with the protocol, must be performed before starting the study treatment where applicable. The same methods that detect lesions at baseline will be used to follow these lesions throughout the study. To ensure compatibility, the radiological assessments used to assess response must be performed using identical techniques. Imaging based evaluation is preferred to evaluation by clinical examination when both methods have been used to assess the anti-tumour effect of a treatment.

Baseline evaluations

These will include radiological measurements of the extent of disease by CT scan or PET-CT scans and endoscopy will also be performed. All areas of disease present must be mentioned (even if specific lesions are not going to be followed for response) and the measurements of all measurable lesions must be recorded on the scan reports. Any non-measurable lesions must be stated as being present.

Evaluations during treatment and at off-study

Tumour assessment will be repeated as per the schedule of events given or more frequently if clinically indicated. All lesions measured at baseline must be measured at subsequent disease assessments, and recorded on the scan reports. All non-measurable lesions noted at baseline must be reported as present or absent. Investigators must ensure that their radiologists are aware of the requirement to follow up and measure every target lesion mentioned at baseline and comment on the non-target lesions in accordance with RECIST (V1.1) criteria.

13.2 Tumour response

To be assigned a status of CR or PR, changes in tumour measurements must be confirmed by two consecutive observations. To be assigned a status of stable disease (SD), follow-up measurements must have met the SD criteria at least once and at least six weeks after study treatment is started. Should rapid tumour progression occur before the completion of treatment the patient will be classified as having early progression (EP). Tumour response should be classified as "not evaluable" (NE), only when it is not possible to classify it under another response category, e.g., when baseline and/or follow-up assessment is not performed or not performed appropriately. The applicable overall response category for each visit that includes disease assessment must be recorded in the medical record for inclusion in the appropriate CRF in OpenClinica.

13.3 Other definitions of outcome:

Toxic death: Any death to which drug toxicity is thought to have a major contribution.

Early death: Death during the first three weeks of treatment that is not a toxic death.

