Screening assessments ¹	X																							
M6620 (Berzosertib) schedule assignment		X																						
Radiotherapy planning	X																							
Radiotherapy (35GY in 15#)			X	X	X	X	X		X	X	X	X			X	X	X	X	X					
M6620 (Berzosertib)				X				X ²		X			X ²			X				X ³				
Haematology/Biochemistry ⁴	X		X			X ²			X			X ²			X			X ³			X			
Coagulation	X		X																			X		
DLT assessment ⁵						X			X			X ²			X			X ³			X	X		
AE assessment ⁵			X			X			X			X ²			X			X ³			X	X	X	
Concurrent medications ⁵	X		X			X			X			X ²			X			X ³			X	X	X	
Physical exams ⁵	X		X			X			X			X ²			X			X ³			X	X	X	
Weight ⁵	X		X						X						X						X	X	X	
ECOG performance status	X		X			X ²			X			X ²			X			X ³			X	X	X	
ECG ⁶	X		X																		X		X	
Vital signs	X											X ⁷												
CT chest abdomen pelvis	X ⁸																					X ¹⁰		
Collection of archival biopsy																							X ¹¹	

¹ Screening assessments including: pregnancy test (to be repeated for WOCBP 4 weekly during treatment), height and medical history, see section 5.3

² Dose schedules -2, -1, 2, 3, 5 & 6 only

³ Dose schedules -1, 3 & 6 only

⁴ Screening and within 24 hours prior to dosing with M6620 (Berzosertib): Haemoglobin, ANC, lymphocytes, WBC, Platelets, Bilirubin, ALP, AST or ALT, urea, Serum creatinine, eGFR, K⁺, Na⁺

⁵ +/- 24 hours, must be prior to dosing with M6620 (Berzosertib); day 4 all patients (excluding weight day 4)

⁶ ECG to be carried out at screening, baseline (pre-M6620 (Berzosertib)) week 4 and week 12 and if clinically indicated on treatment

⁷ Per clinical requirement

⁸ Screening CT only needs to be done if diagnostic CT carried out > 42 days prior to start of treatment

⁹ Week 4 follow-up should be 1 week after last dose/fraction (+7 days)

¹⁰ CT Scan can be done up to 7 days prior to the Week 12 visit

¹¹ Optional

SUMMARY SCHEDULE OF EVENTS STAGE A2

	Post Registration	Cycle 1*			Cycle 2			Cycle 3			Cycle 4		Cycles 5-6 ¹⁰		Follow up ¹¹	
		Week 1	Week 2	Week 3	Week 4	Week 5	Week 6	Week 7	Week 8	Week 9	Week 10	Week 11	Week 12	8 weeks post EOT	2 weeks post EOT	
Informed Consent	X															
Screening assessments ¹	X															
M6620 (Berzosertib) schedule assignment		X														
Capecitabine ²			X	X	X	X	X	X	X	X	X	X	X	X		
Cisplatin ³				X ³		X ³			X ³				X ³			
M6620 (Berzosertib) ⁴				X ⁴												
Haematology/Biochemistry ⁵	X		X	X	X	X	X	X	X	X	X	X	X	X	X	X
Coagulation	X		X												X	
ECOG performance status ⁶	X		X	X	X	X	X	X	X	X	X	X	X	X	X	X

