2.4 Duration of patient participation

Stage A1: Participants will be in the study for 12 weeks from first trial dose or intervention to last protocol visit.

[figure not shown]
Stage A2: Participants will be in the study for maximum of 26 weeks from first trial dose to last protocol visit.

Stage B: Participants will be in the study for 24 weeks from first trial dose or intervention to last protocol visit.

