5.4 Stage A Evaluations

5.4.1 Stage A1 evaluations during the study

Post registration and prior to start of Radiotherapy

- M6620 (Berzosertib) schedule assignment
- Radiotherapy planning (or pre-registration during screening)

Evaluations Week 1:

The following assessments should be done Day 1 and Day 4 (+/-24 hours but must be pre-M6620 (Berzosertib)) unless stated otherwise:

- Venous blood sample within 24 hours prior to M6620 (Berzosertib) including:
 - Haematology – Haemoglobin, white blood cells (WBC) with differential count (neutrophils and lymphocytes) and platelets

- Biochemistry – sodium, potassium, urea, creatinine, bilirubin, ALP, AST or ALT
- Coagulation – INR, APTT or PTT.
- Adverse Event (AE) Assessment
- Assessment of concomitant medications
- Physical examination
- Weight (Day 1 only)
- ECOG performance status
- Assessment of DLT (Day 4 only)
- ECG (Day 1 prior to treatment)
- On days of M6620 (Berzosertib) monitor patient for reactions for 20 minutes after administration

Evaluation during radiotherapy and concomitant M6620 (Berzosertib) (Weeks 2 - 3)

The following assessments should be done the day before each administration of M6620 (Berzosertib) (+/-24 hours but must be pre-M6620 (Berzosertib)) unless stated otherwise:

- Venous blood sample within 24 hours prior to administration of M6620 (Berzosertib) including:
 - Haematology – Haemoglobin, white blood cells (WBC) with differential count (neutrophils and lymphocytes) and platelets
 - Biochemistry – sodium, potassium, urea, creatinine, bilirubin, ALP, AST or ALT
- Assessment of AE
- Assessment of concomitant medications
- Physical examination
- Weight (Day 8 & 15 only)
- ECOG performance status
- Assessment of DLT
- On days of M6620 (Berzosertib) monitor patient for reactions for 20 minutes after administration

Evaluations on Week 4, 9 & 12

- Assessment of AE
- Assessment of concomitant medications
- Physical examination
- Weight
- ECOG performance status
- Assessment of DLT (not week 12)
- Coagulation – INR, APTT or PTT (week 4 only)
- Haematology – Haemoglobin, white blood cells (WBC) with differential count (neutrophils and lymphocytes) and platelets (week 4 only)
- Biochemistry – sodium, potassium, urea, creatinine, bilirubin, ALP, AST or ALT (week 4 only)ECG (weeks 4 & 12 only)
- CT chest, abdomen, pelvis (week 12 only). If disease progression is already identified by CT scan during the follow up period, a repeat CT scan is not necessary at week 12.

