 - Haematology – Hb, white blood cells (WBC) with differential count (neutrophils and lymphocytes) and platelets
 - Biochemistry – sodium, potassium, urea, creatinine, bilirubin, ALP and AST or ALT, Ca, Mg, Phosphate
- Assessment of concomitant medications
- ECOG performance status
- Vital signs: systolic/diastolic blood pressure (BP), pulse rate, temperature
- Coagulation (INR, APTT or PTT, week 12 only)
- Physical examination
- Mellow score
- Assessment of AE
- Assessment of DLT
- Research blood sample (week 12 only)

Evaluations at week 24

- Assessment of concomitant medications
- ECOG performance status
- Vital signs: systolic/diastolic blood pressure (BP), pulse rate, temperature
- Physical examinations
- ECG
- Mellow score
- Assessment of AE
- Assessment of DLT
- Endoscopy and research biopsy
- CT chest abdomen and pelvis to assess response

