- **Ultrasound.** Ultrasound is not useful in assessment of lesion size and should not be used as a method of measurement. If new lesions are identified by ultrasound in the course of the study, confirmation by CT should be obtained.
- **Endoscopy, Laparoscopy.** The utilization of these techniques for objective tumour evaluation is not advised. However, they can be useful to confirm complete pathological response when biopsies are obtained or to determine relapse in trials where recurrence following complete response or surgical resection is an endpoint.
- **Tumour Markers.** Tumour markers alone cannot be used to assess objective tumour response. If markers are initially above the upper normal limit, however, they must normalize for a patient to be considered in complete response.
- **Cytology, Histology.** These techniques can be used to differentiate between PR and CR in rare cases if required by protocol (for example, residual lesions in tumour types such as germ cell tumours, where known residual benign tumours can remain). When effusions are known to be a potential adverse effect of treatment (e.g.

with certain taxane compounds or angiogenesis inhibitors), the cytological confirmation of the neoplastic origin of any effusion that appears or worsens during treatment when the measurable tumour has met criteria for response or stable disease is advised to differentiate between response or stable disease and progressive disease.

B.2 Tumour response evaluation

All patients will have their BEST RESPONSE from the start of study treatment until the end of treatment classified as outlined below:

Complete or partial responses may be claimed only if the criteria for each are met at a subsequent time point at least 4 weeks later. Refer to the table B1 and table B2 below.

Complete Response (CR): disappearance of all *target* and *non-target* lesions and normalization of tumour markers.

Pathological lymph nodes must have short axis measures < 10 mm (Note: continue to record the measurement even if < 10 mm and considered CR). Tumour markers must have normalized. Residual lesions (other than nodes < 10 mm) thought to be non-malignant should be further investigated (by cytology or PET scans) before CR can be accepted.

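### Stages A1 and B schedule one response CT each, so CR/PR cannot be confirmed from scheduled scans, and the label for a single responding scan is not settled

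*Protocol*

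**What the plan says.** Protocol 13.2 sets the rule: "To be assigned a status of CR or PR, changes in tumour measurements must be confirmed by two consecutive observations". Appendix B.2 adds the interval: "Complete or partial responses may be claimed only if the criteria for each are met at a subsequent time point at least 4 weeks later". It also sets the period over which response is judged: "All patients will have their BEST RESPONSE from the start of study treatment until the end of treatment classified as outlined below".

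Stage A1 has one post-baseline CT, at week 12 (section 5.4.1). Footnote 10 of the A1 schedule of events says "CT Scan can be done up to 7 days prior to the Week 12 visit". Section 5.4.1 also says: "If disease progression is already identified by CT scan during the follow up period, a repeat CT scan is not necessary at week 12". Section 2.4 places the last visit at the same time: "Stage A1: Participants will be in the study for 12 weeks from first trial dose or intervention to last protocol visit".

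For Stage B, section 5.5.1 lists "CT chest abdomen and pelvis to assess response" under week 24 and lists no CT at weeks 12 or 18. Appendix B.2.1 likewise gives baseline and 24 weeks only. Section 2.4 again places the last visit there: "Stage B: Participants will be in the study for 24 weeks from first trial dose or intervention to last protocol visit".

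Stage A2 has CTs at weeks 6, 12 and 18 and at 8 weeks after the end of treatment. Section 13.1 allows additional assessments in any stage when clinically indicated.

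SAP 7.2.2 reports CR, PR, SD and PD overall and by schedule for all stages, and SAP 5.2 sends the classification to protocol Appendix B.

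**The concern.** The plan asks for two assessments but schedules one in two of its three stages. When the second is missing, several parts of the protocol could supply the category, and they disagree: the endpoint tables in section 3, Table B1, Table B2 and Appendix B.3. The SAP does not choose between them, so the choice could be made after open-label scans have been seen.

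The reported response rate depends on that choice. Because A2 can confirm responses and A1 and B cannot, applying Appendix B uniformly would also produce rates that mean different things in different stages.

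**Working it through.** **1. Scheduled scans.** CT times come from sections 5.4.1, 5.4.4 and 5.5.1 and the A1 and A2 schedule footnotes; last visits from section 2.4; treatment durations from the synopsis. The Stage B schedule table was not readable in the copy used, so the Stage B row rests on section 5.5.1 and Appendix B.2.1.

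| Stage | Post-baseline response CTs (week) | Last visit | End of treatment | Earliest confirming CT | Scheduled consecutive pairs at least 4 weeks apart |
|---|---|---|---|---|---|
| A1 | 12 (11 at the earliest) | 12 | 3 | 11 + 4 = 15 to 12 + 4 = 16 | 0 |
| B | 24 | 24 | 11 | 24 + 4 = 28 | 0 |
| A2 (six cycles) | 6, 12, 18, 26 | 26 | 18 | 12, for a response first seen at week 6 | 3 (gaps 6, 6, 8) |

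The 6- and 12-month follow-up in A1 collects clinician-reported progression, death, events and further treatment, with no scheduled CT. Stage B endoscopy does not fill the gap. The week 24 procedure is at the same time point as the CT, the week 7 one is a research procedure during treatment, and Appendix B.1.2 advises against endoscopy for objective evaluation.

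**2. Best-response window.** If the window closes at the end of treatment, the only A1 CT falls 11 − 3 = 8 to 12 − 3 = 9 weeks after it, and the only Stage B CT 24 − 11 = 13 weeks after it. The last A2 CT is also outside, by 26 − 18 = 8 weeks.

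**3. Label for one responding scan, in a patient with target lesions.**

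| Source | CR-appearance scan | PR-appearance scan |
|---|---|---|
| Endpoint tables (response at week 12 / 24); Table B1 (documented once) | CR | PR |
| Appendix B.3 (response not confirmed) | PR | unknown |
| Table B2, if the absent second scan is read as NE | SD | SD |

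Three details fix these entries. A CR-appearance scan has necessarily shrunk by the 30% needed for PR, so B.3's exception for an unconfirmed CR applies and unknown is not reached. A PR-appearance scan fails the SD definition, which excludes PR-level shrinkage, so B.3 gives unknown. Weeks 12 and 24 both pass the six-week minimum for SD in section 13.2, so Table B2's fallback to NE is not reached. Table B2 has no row for a second scan that was never scheduled, and the extra-requirements column of Table B1 may add to the confirmation rule rather than replace it.

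**4. Effect on the rate.** Let c be the number of CR-appearance scans, p the number of PR-appearance scans and n the number of patients.

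- Single-scan reading: (c + p)/n
- B.3: c/n, every one of them recorded as PR
- Table B2 with the absent scan as NE: 0/n

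The documents give no expected response counts, so these are assumed, at maximum enrolment:

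- A1, n = 20, c = 2, p = 4: 6/20 = 30%, 2/20 = 10%, 0/20 = 0%
- B, n = 25, c = 5, p = 5: 10/25 = 40%, 5/25 = 20%, 0/25 = 0%

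**5. Denominator.** SAP 5.2 first makes all treated patients evaluable for response, then only those with measurable disease, at least one cycle and a re-evaluation. Protocol 6.3 does the same, with its first statement limited to Stage B. Appendix B.3 requires every included patient to be assessed, even if not re-evaluated. If a fraction m is not re-evaluated, the re-evaluated-only rate is 1/(1 − m) times the all-treated rate on the single-scan reading. For an assumed m of 10% to 25%, that is 1/0.90 = 1.11 to 1/0.75 = 1.33.

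**The case against.** The strongest reply is that the stage-specific text governs. The endpoint tables fix response at week 12 in A1 and week 24 in B, SAP 7.2.2 does not mention best response, and Appendix B describes itself as a quick reference. A sensible analyst would report the category at that visit. This is a reasonable reading and is close to the fix proposed here. But the confirmation rule also stands in the body of the protocol, at 13.2, SAP 5.2 sends classification to Appendix B, and nothing says that the endpoint tables override either.

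A second reply is that the text does settle a PR-appearance scan: 13.2 gives a follow-up assessment that was not performed as an example of NE, and Table B2 turns PR followed by NE into SD. That route exists. Whether a scan that was never planned counts as not performed is arguable, and B.3 gives a different answer.

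Some of the reply on related text stands. The B.2.1 scan times conflict with A1 and A2, but those times are explicit elsewhere, so sites are unlikely to be misled. On the denominator, 6.3 and SAP 5.2 keep patients who progress before the end of cycle 1, B.3 has early-death categories, and SAP 7.2.2 asks for the number of participants in each analysis. These soften the conflict but do not select a denominator. Counting patients without re-evaluation as non-responders is a convention, not something the documents require.

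**Conclusion.** The point holds, and should be fixed. Scheduled scans supply 0 confirming pairs in A1 and 0 in Stage B, against 3 in A2. With target lesions, a single responding scan has three possible labels. SAP 7.2.2 has no row for unknown or NE, and the denominators contradict each other. The counts follow from the text; the percentages in the working rest on assumed numbers and only show how far the readings diverge.

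A reader might infer more than the documents support:

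- That no confirmed response is possible at all. Section 13.1 allows clinically indicated CTs, so the limit applies to scheduled scans.
- That enforcing confirmation gives a response rate near zero whatever the scans show. B.3 keeps an unconfirmed CR as PR. What is lost is every PR-appearance scan and the CR category itself.
- That a CR-appearance scan could also be unknown, making four labels. With target lesions it always meets the PR criteria, so three remain.

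The consequence is limited to a descriptive secondary endpoint. The DLT endpoint, schedule allocation, sample size and safety analyses do not use it.

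**What to change.** 1. For A1 and B, define objective response as the RECIST 1.1 category at the scheduled week 12 or week 24 CT, reported as unconfirmed. Count earlier documented progression as PD; this is needed because A1 patients with CT-proven progression may skip the week 12 scan.
2. State that the confirmation rule and Table B2 apply to A2 only.
3. Extend the best-response window to each stage's last scheduled response CT: week 12 in A1, 8 weeks after the end of treatment in A2, week 24 in B. List the CT times by stage in B.2.1.
4. State one denominator in protocol 6.3, Appendix B.3 and SAP 5.2 and 7.2.2, and add an unknown/NE row to the SAP table.

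No extra scans or data are needed, since 13.2 already has the response category at each assessed visit recorded for the CRF. The protocol wording needs an amendment. The SAP update already promised before Stage B opens can carry the SAP part for Stage B. The scientific cost is that unconfirmed response is a more lenient measure. Keeping confirmation instead would need a further CT at week 15–16 or later in A1 and week 28 or later in B, beyond the current last visits.
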